9.4.5 Physical Measurements

Physical measurements including height, weight and BMI will be performed at screening (Section 2).

Measurement of height should be performed with the participant's shoes removed, pockets emptied and no overcoat. The participant's knees should be straightened, head held erect, and eyes forward. Weight must be recorded using a calibrated scale.

BMI is a method of defining normal body weight and excess body fat. Method of BMI calculation is as follows:

- Use actual height and weight
 - To calculate BMI:
 - BMI = weight $(kg)/(height [m])^2$
 - Round to 1 decimal place (if 0.05 or greater, round up)

The BMI calculation is used for assessment for inclusion. All analysis calculations for BMI will be derived internally using the weight and height at the specified time point or the most recent height measurement (if not applicable).

9.5 Pharmacokinetics

Pharmacokinetics of milvexian and [14C] milvexian, as applicable, will be derived from plasma concentration vs time and urinary excretion data. The pharmacokinetic parameters to be assessed include:

F	Absolute oral bioavailability (oral versus IV)
Cmax	Maximum observed plasma concentration
Tmax	Time of maximum observed plasma concentration
AUC(0-T)	Area under the plasma concentration-time curve from time zero to time of last quantifiable concentration
AUC(INF)	Area under the plasma concentration-time curve from time zero extrapolated to infinity
Ae	Amount of unchanged drug excreted into the urine
%UR	Percent urinary recovery
T-HALF	Terminal plasma half-life
CLT	Total clearance
CLT/F	Apparent clearance of drug after extravascular administration
CLR	Renal clearance

Frel	Relative bioavailability based on Cmax, AUC(0-T) and AUC(INF)
MRT	Mean residence time
Vss	Volume of distribution at steady state
Vz	Volume of distribution of terminal phase
Vz/F	Apparent volume of distribution at terminal phase after extravascular administration

Individual participant PK parameter values will be derived by noncompartmental methods by a validated PK analysis program. Actual times will be used for the analyses.

Table 9.5-1Table 9.5-2ist the sampling schedules to be followed for the assessment of pharmacokinetics in the plasma and urine, respectively.

Table 9.5-1: Pharmacokinetic Plasma Sampling Schedule for Milvexian Treatment Periods ()

Study Day of Sample Collection	Event	Time (Relative To Milvexian Dose/Oral Dose) Hour:Min	Milvexian Blood Sample (for LC-MS/MS analysis)	[¹⁴ C]Milvexian Blood Sample (for AMS analysis) ^a
	Predose	00:00	X	X
	Post dose	00:30	X	
	Post dose/SOI	01:00 ^b	X	
	Post dose	01:05 ^a		X
	Post dose	01:10 ^a		X
	Post dose/EOI	01:15	X	X ^c
	Post dose	01:20ª		X
	Post dose	01:30	X	X
	Post dose	01:45ª		X
	Post dose	02:00	X	X
	Post dose	03:00	X	X
	Post dose	04:00	X	X
	Post dose	05:00	X	X
	Post dose	06:00	X	X
	Post dose	08:00	X	X
	Post dose	10:00	X	X
	Post dose	12:00	X	X
	Post dose	14:00	X	X
	Post dose	18:00	X	X

Table 9.5-1: Pharmacokinetic Plasma Sampling Schedule for Milvexian Treatment Periods ()

Study Day of Sample Collection	Event	Time (Relative To Milvexian Dose/Oral Dose) Hour:Min	Milvexian Blood Sample (for LC-MS/MS analysis)	[¹⁴ C]Milvexian Blood Sample (for AMS analysis) ^a
	Post dose	24:00	X	X
	Post dose	36:00	X	X
	Post dose	48:00	X	X
	Post dose	72:00 ^d	X	X

AMS: accelerator mass spectrometry; EOI: End of infusion; LC-MS/MS: liquid chromatography mass spectrometry/mass spectrometry; SOI: Start of infusion

Table 9.5-2: Pharmacokinetic Urine Sampling Schedule for Milvexian (Treatment Periods)

Study Day of Sample Collection	Event	Time (Relative To Milvexian Dose/Oral Dose) Hour:Min	Milvexian Urine Sample (for LC-MS/MS analysis)
	Predose ^a	00:00	X
	0 to 6 h	06:00	X
	6 to 12 h	12:00	X
	12 to 24 h	24:00	X
	24 to 36 h	36:00	X
	36 to 48 h	48:00	X
	48 to 72 h	72:00 ^b	X

^a A single urine sample will be taken at predose (or the first void of the day).

All on-treatment timepoints are intended to align with days on which study intervention is administered. If it is known that a dose is going to be delayed, then the predose sample for milvexian, if appropriate, should be collected just prior to the delayed dose. However, if a predose milvexian sample is collected but the dose is subsequently delayed, an additional predose sample should not be collected. Blood samples should be drawn from a site other than the infusion site (ie,

^a Treatment Period (IV microdose regimen) only.

b The SOI blood sample for LC-MS/MS analysis will be taken prior to administration of the microdose.

^c This sample should be taken immediately after stopping the IV infusion. If the end of infusion is delayed, the collection of this sample should also be delayed.

d Where Day of a treatment period coincides with the 72 hour time point of the previous treatment period, only a single predose/72 hour post dose sample is required.

b Where Day of a treatment period coincides with the 72 hour time point of the previous period, only a single 72 hour post dose collection is required.

contralateral arm) on days of infusion. If the infusion was interrupted, the interruption details will also be documented on the CRF. Further details of the PK blood and urine sample collection, labeling, processing, storage, and shipment will be provided in the laboratory/procedure manual.

The plasma samples will be analyzed for milvexian by a validated liquid chromatography mass spectrometry/mass spectrometry (LC-MS/MS) assay or by a qualified accelerator mass spectrometry (AMS) assay (analyzed according to the PK sampling schedule described in Table 9.5-1). Milvexian in urine will be analyzed by a validated LC-MS/MS assay.

Bioanalytical samples designated for assessments from the same collection time point may be used interchangeably for analyses, if needed.

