7.1 Study Interventions Administered

The selection and timing of dose for each participant is as follows:

Table 7.1-1: Study Interventions

Intervention Name	BMS-986177 oral solution mg	BMS-986177 SDD capsules, mg	[14C]BMS-986177 Solution for Infusion µg/mL (NMT kBq/ mL)
Dose Formulation	Solution	SDD Capsules	Solution for IV infusion
Unit Dose Strength(s)	8		μg/mL
Dosage Level(s)	mg dose	mg dose AND mg dose (as mg capsules)	μg dose
Route of Administration	Oral, fasted	Oral, fasted AND fed	IV infusion, fasted
Sourcing	Prepared by the trial site	Provided centrally by the Sponsor	Prepared by the trial site
Packaging and Labeling	The oral solution will be provided in bulk container. Each bulk container will be labeled as required per country requirement.	Study intervention will be provided in a bottle. Each bottle will be labeled as required per country requirement	Study intervention will be provided in a bulk container. Each bulk container will be labeled as required per country requirement

In the morning of Treatment Period, Day, after fasting for at least 10 hours, each participant will receive a oral dose of milvexian oral solution, which will be followed by appropriate rinses and additional water, for a total volume of 240 mL. The time of dose administration will be called "0" hour. At 1 hour post dose (approximately Tmax), participants will receive an IV microdose of [14C]milvexian solution for infusion over 15 minutes.

For IV dosing only: the IV dose will be infused over approximately 15 minutes. This infusion will be in the opposite arm being used for PK sampling.

To assess tolerability of the IV administration, the first participant will be dosed at least 30 minutes prior to dosing the second participant. All subsequent dosing of the IV formulation will be staggered by at least 15 minutes. To allow for potential interruptions and pump variations, up to a 20% difference in duration of the infusion will not be considered a protocol deviation provided the full planned dosed is administered as these minor discrepancies should not have a significant impact on the overall study objectives.

The planned infusion time will be 15 minutes; the actual infusion start and stop time will be recorded in the source.

• The infusion will finish within ± 3 minutes of the nominal time point

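### Does timing the [14C]milvexian samples from the oral dose inflate the IV AUC and so understate absolute bioavailability?

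*Combined protocol and SAP*

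**What the plan says.** Section 7.1 fixes the clock for the solution period by the oral dose: "The time of dose administration will be called" hour zero. It then places the IV dose on that clock: "At 1 hour post dose (approximately Tmax), participants will receive an IV microdose of [14C]milvexian solution for infusion over 15 minutes". Table 9.5-1 lists LC-MS/MS and AMS samples against the same column, "Time (Relative To Milvexian Dose/Oral Dose) Hour:Min". The AMS samples nearest the infusion start are at 00:00 and 01:05. The 01:00 row is marked for LC-MS/MS only, and its footnote reads "The SOI blood sample for LC-MS/MS analysis will be taken prior to administration of the microdose".

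Section 9.5 defines AUC(INF) as "Area under the plasma concentration-time curve from time zero extrapolated to infinity", without saying which zero applies to [14C]milvexian. It gives no formula for MRT or Vss and mentions no correction for infusion length.

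Several other provisions bear on the point:
- Parameters come from a validated noncompartmental program, and "Actual times will be used for the analyses".
- Section 7.1 has the site record when each infusion really began and ended.
- Table 9.5-1 labels the start and end of infusion, and the end-of-infusion sample moves if the infusion runs late.
- Section 9.5 also says "Bioanalytical samples designated for assessments from the same collection time point may be used interchangeably for analyses, if needed".
- Section 10.4 defers the detailed SAP to a separate document, due before database lock, which is not in the file.

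**The concern.** The IV AUC is the denominator of F for all five treatments, and F is the only primary endpoint. Read literally, the only stated zero lies an hour before any [14C] is given. On that clock the first AMS interval lasts 65 minutes, although drug is entering for only the last 5. A linear trapezoid across it adds area that does not exist. The error would have the same sign in every participant, so averaging would not remove it.

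MRT, a named secondary endpoint, would also be measured from the wrong origin. Vss, which is normally obtained from it, would be affected too. IV Tmax would read about 1.25 h when the infusion lasts 0.25 h. A missing AMS sample at 01:00 seems to make the first error harder to avoid.

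**Working it through.** **The plan's own figure.** The only computed design figure is in Section 10.2: with 13 evaluable participants and an intra-subject CV of 28.3%, an 80% probability that the 90% CI lies within 80% to 125% of the estimated ratio.
- SD on the log scale = sqrt(ln(1 + 0.283²)) = 0.278.
- 90% CI half-width at that SD, paired on 12 df = t(0.95, 12) × 0.278 × sqrt(2/13) = 0.194.
- Probability = P(chi-square on 12 df ≤ 12 × (ln 1.25 / 0.194)²) = 0.803.

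The figure reproduces, and the IV clock does not enter it. The documents state no figure for IV AUC, MRT or F.

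**Inputs for the clock question.** From the documents: infusion start 01:00, duration T = 0.25 h, the AMS times of Table 9.5-1, and terminal half-lives of 9.04 to 12.2 h from the oral data in Section 3.2.1. Assumed, because IV disposition is not given: one compartment, or two compartments with distribution half-life 0.25 to 1 h and intercept ratio A/B of 2 to 10.

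**The false area.** Oral clock, 00:00 joined to 01:05: ½ × (65/60) × C(01:05). True clock, zero at infusion start: ½ × (5/60) × C(01:05). The difference is 0.5 h × C(01:05).

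**One compartment in closed form.** With k = ln 2 / half-life, C(01:05) = (rate/CL)(1 − e^(−k/12)) and AUC(INF) = rate × 0.25/CL. The relative inflation is therefore 2(1 − e^(−k/12)).
- Half-life 9.04 h: k = 0.0767, inflation 1.27%.
- Half-life 12.2 h: k = 0.0568, inflation 0.94%.

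**Full noncompartmental runs.** These use linear-up/log-down trapezoids and MRT = AUMC/AUC − T/2. The table compares the literal oral clock with time counted from the infusion start (concentration 0 there).

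| Profile | IV AUC | F | MRT, infusion-start to oral clock |
|---|---|---|---|
| 1-cpt, 9.04 h | +1.27% | −1.26% | 13.04 to 13.88 h (+6.4%) |
| 1-cpt, 10.5 h | +1.10% | −1.09% | 15.15 to 15.98 h (+5.5%) |
| 1-cpt, 12.2 h | +0.94% | −0.94% | 17.60 to 18.44 h (+4.7%) |
| 2-cpt, smallest AUC effect | +2.4% | −2.3% | 15.30 to 15.94 h (+4.2%) |
| 2-cpt, largest AUC effect | +9.9% | −9.0% | 10.22 to 10.30 h (+0.8%) |

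Across all two-compartment cases MRT changes by −0.4% to +8.3%. Across all cases Vss changes by −8.3% to +5.1%. Leaving out the half-infusion correction as well adds 0.125 h to MRT, which takes the 9.04 h one-compartment case from +6.4% to +7.4%.

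**Two other calculations.**
- Oral clock with a zero entered at 01:00: no false area, F unchanged, MRT too long by exactly 1.0 h. The AUC error and the full extra hour of MRT therefore do not occur together.
- Time counted from the infusion start, concentration 0 there: AUC(INF) within 0.0% to +0.8% of true, MRT within 0.1 h of true.

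**Which calculation does the plan call for?** The AUC bias needs two choices: keeping the oral dose as origin for an analyte given an hour later, and drawing a trapezoid across an hour in which no [14C] had been given. No passage states either. Table 9.5-1 is a collection schedule shared by two assays, and a collection clock does not fix the origin of the analysis. The recorded infusion times supply the right origin. The absent AMS sample costs nothing: [14C] is given on one occasion, so the concentration just before the infusion is zero. A blood sample is drawn at that moment anyway and could be assayed.

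**The case for a change.** The strongest reply is that using actual times replaces nominal times with real ones but does not say since what, and the only zero the protocol names is the oral dose. Interchangeable use of samples is permitted only where needed, and no AMS assay at 01:00 is scheduled. Entering a zero at 01:00 repairs AUC but leaves MRT an hour too long; only moving the origin repairs both. Section 10.4 describes the coming SAP in terms of participant selection and missing, unused and spurious data, not the IV time origin. Two sentences would settle it, for the denominator of the primary endpoint.

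The textual part stands: Section 9.5 is silent, and writing the convention down would do no harm. It does not follow that the results will be wrong. Mean residence time and clearance after an IV dose are defined relative to that dose, so an analyst sets the infusion start as the origin without being told. A slip would also be visible, as an IV Tmax of about 1.25 h after a 15-minute infusion. Every input for the correct calculation is already collected, and a SAP that is not in the file cannot be faulted for what it leaves out.

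**Conclusion.** The concern describes a possible mistake that the plan does not prescribe. If it were made, F would be understated by 0.9% to 1.3% (relative) with one compartment and by 2.3% to 9.0% under the assumed two-compartment range, and MRT would typically be up to about 0.8 h too long. The upper figures rest wholly on assumed IV disposition. The relative bioavailability and food-effect ratios use oral exposures only and would not move. Ratios of F between treatments would not move either, because all share one IV reference.

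With time counted from the recorded start of infusion, the error is at most 0.8% in AUC and 0.1 h in MRT under the same assumptions. The unstated origin, half-infusion correction and Vss formula are standard details that a pharmacokinetic analyst fills correctly from data the plan already collects. No change is needed.

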9.6 Immunogenicity Assessments

Not applicable.

9.7 Genetics

Not applicable.

9.9 Additional Research

This protocol will not include sample collection and/or residual sample storage for additional research.

9.10 Other Assessments

Not applicable.

9.11 Health Economics

Health economics/medical resource utilization and health economics parameters will not be evaluated in this study.

10 STATISTICAL CONSIDERATIONS

10.1 Statistical Hypotheses

No prospective hypotheses are being formally evaluated.

10.2 Sample Size Determination

Sample size determination is based on consideration of the precision of the estimate of the geometric mean ratios (GMR) of Cmax and AUCs of milvexian between test and reference treatments. With 13 evaluable participants, there will be an 80% probability that the 90% confidence interval (CI) of GMR will be within 80% and 125% of the point estimate. The precision estimate is based on the assumptions that Cmax and AUCs of milvexian are log-normally distributed with intra-subject coefficient of variation (CV) of no greater than 28.3%.

A sample size of 16 participants to achieve 13 evaluable participants is considered appropriate to meet the objectives of the study.

10.3 Analysis Sets

For the purposes of analysis, the following populations are defined:

Population	Description	
Enrolled	All participants who have agreed to participate in a clinical study following completion of the informed consent process	
Treated	All participants who received at least 1 dose of study intervention. This population will be used for the safety analyses	
PK	All randomized participants who receive at least 1 dose of study drug and have any available concentration-time data	
Evaluable PK	The Evaluable PK Population includes all participants in the PK Population with adequate PK profiles for accurate estimation of PK parameters	

10.4 Statistical Analyses

The statistical analysis plan (SAP) will be developed and finalized before database lock and will describe the selection of participants to be included in the analyses and procedures for accounting for missing, unused, and spurious data. Below is a summary of planned statistical analyses of the primary and secondary endpoints.

A description of the participant population will be included in the clinical study report, including subgroups of age, gender, race and other study specific populations and demographic characteristics. A description of participant disposition will also be included in the clinical study report.

10.4.1 Primary Endpoint

Pharmacokinetic results will be listed for the PK Population; descriptive summary statistics will use the Evaluable PK Population

Table 10.4.1-1: Primary Endpoint

Primary Endpoint	Description	Timeframe
Pharmacokinetics – F	Absolute oral bioavailability (F) for each treatment will be summarized, and descriptive statistics and 90% CI for F will be presented	Following oral dose on separate occasions and a oral dose followed by an IV injection on a occasion (i.e., Day of Period)

10.4.2 Secondary Endpoints

Table 10.4.2-1: Secondary Endpoints

Secondary Endpoint	Description	Timeframe	
Pharmacokinetics – Cmax, Tmax, AUC(0-T), AUC(INF), CLT or CLT/F, CLR, Vz or Vz/F, Ae, %UR, T-HALF, for each treatment	Summary statistics by treatment will be tabulated for plasma concentrations and PK parameters of milvexian and [14C]milvexian, as applicable. Geometric means and coefficients of variation (CV%) will be presented for Cmax, AUC(0-T), AUC(INF), CLT or CLT/F, CLR, Vz or Vz/F, Ae, %UR. Medians and ranges will be presented for Tmax. Means and standard deviations (SDs) will be presented for T-HALF.	Following oral dose on separate occasions and a oral dose followed by an IV injection on a single occasion (i.e., Day of Period)	
Pharmacokinetics – MRT and Vss of [14C]milvexian following an IV dose	Summary statistics by treatment will be tabulated for plasma concentrations and PK parameters of ¹⁴ C]milvexian. Geometric means and coefficients of variation (CV%) will be presented for MRT and Vss.	Following oral dose on separate occasions and a oral dose followed by an IV injection on a occasion (i.e., Day of Period)	
Pharmacokinetics – Frel for each SDD capsule treatment vs oral solution formulation	Point estimates and 90% CI for the ratio of geometric means for Cmax, AUC(0-T) and AUC(INF) will be constructed for the comparison of: • each milvexian capsule treatment separately versus mg oral solution A linear mixed-effect model will be used on log transformed data with treatment and period as fixed effects, and measurements within each participant as repeated measures.	Following oral dose on separate occasions and a oral dose followed by an IV injection on a occasion (i.e., Day of Period)	
Pharmacokinetics – Food effect with mg and mg SDD capsules based on ratios of Cmax, AUC(0-T), and AUC(INF)	Point estimates and 90% CI for the ratio of geometric means for Cmax, AUC(0-T) and AUC(INF) will be constructed for the comparison of: • mg SDD fed versus mg SDD fasted • mg SDD fed versus mg SDD fasted A linear mixed-effect model will be used on log transformed data with treatment and period as fixed effects, and measurements within each subject as repeated measures.	Following oral dose on separate occasions and a oral dose followed by an IV injection on a occasion (i.e., Day of Period)	

Table 10.4.2-1: Secondary Endpoints

Secondary Endpoint	Description	Timeframe
Safety – Occurrence of AEs and SAEs, abnormalities in vital sign measurements exceeding pre-defined thresholds, findings on ECGs and physical examinations, and abnormalities in clinical laboratory tests	All recorded SAEs and AEs will be listed and tabulated by system organ class, preferred term and treatment. Adverse events leading to discontinuation will be listed. All nonserious AEs reported up to the follow up call will be included in the AE summary tables.	Following oral dose on separate occasions and a oral dose followed by an IV injection on a occasion (i.e., Day of Period)
	Any abnormal physical examination findings will be listed.	
	Vital signs and clinical laboratory test results will be listed. The frequency of marked abnormalities in clinical laboratory test results will also be tabulated by treatment.	
	ECG readings will be evaluated by the Investigator and abnormalities, if present, will be listed.	

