3.3.1 Risk Assessment

Table 3.3.1-1: Risk Assessment

Potential Risk of Clinical Significance	Summary of Data/Rationale for Risk	Mitigation Strategy				
Study Interventions						
Exposure to milvexian	oral dose of mg milvexian (as SDD capsules in the fed and fasted state, and as the oral solution) and a dose of mg (as SDD capsule in the fed state), will be dosed across treatment periods in this study	Milvexian has been shown to be safe and well tolerated in healthy participants at doses up to 500 mg daily for 14 days. Only healthy participants will be enrolled in this study (see Sections 6.1 and 6.2). The overall safety profile of milvexian in healthy participants supports clinical evaluation of the PK profile and safety/tolerability of oral doses of mg and mg milvexian in healthy participants. Based on available data, a low risk of bleeding is expected with administration of doses.				
Exposure to radiolabeled intravenous microdose	Participants in this study are exposed to ionizing radiation. It is believed that any increase in the amount of radiation that is received above background radiation carries a risk of later developing serious and possibly fatal conditions	Based on National Radiological Protection Board (NRPB) publication NRPB-R245, the radioactive administrations will result in an effective dose of <0.1 mSv. In comparison, the UK average radiation exposure for an individual is about 2.7 mSv (data obtained from Public Health England [PHE] Ionising Radiation Exposure of the UK Population: 2010 Review) per year and as such the radiation risk to participants in this study is considered negligible.				
Study Procedures						
ECG stickers	Stickers on the participants' chests and limbs may cause some local irritation and may be uncomfortable to remove	Participants will be closely monitored to ensure any local irritation does not persist				

Table 3.3.1-1: Risk Assessment

Potential Risk of Clinical Significance	Summary of Data/Rationale for Risk	Mitigation Strategy	
Collecting blood samples	Collecting a blood sample from a vein may cause pain, swelling, bruising, light headedness, fainting, and very rarely, clot formation, nerve damage and/or infection at the site of the needle stick	Participants will be closely monitored	

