5 STUDY DESIGN

5.1 Overall Design

- This is a Phase 1, open-label, partially randomized, period crossover study to evaluate the absolute bioavailability of milvexian following oral administration of a solution in conjunction with a ¹⁴C microdose given at the Tmax of the oral solution when fasted, and crossover doses of SDD capsules at two dose levels in the fed and fasted state across treatment periods in healthy volunteers. The duration of study participation is expected to be up to approximately 7 weeks (including screening).
- Participants will undergo screening evaluations to determine study eligibility within prior to initial administration of study treatment (Day , Treatment Period). Participants will be admitted to the clinical facility on the morning of Day of Treatment Period and will remain in the facility for the entire duration of the dosing treatment periods, including washout.
- On Day of Treatment Period all participants will be randomized to a treatment sequence, with the treatment for Treatment Period fixed owing to logistical consideration of the radiolabeled investigational product.
- Participants will be randomized to 1 of 4 treatment sequences immediately prior to administration of treatment in Treatment Period. A 4-sequence Latin square, will be used; the treatment sequences are presented in Table 5.1-1.
 Fasted study treatments will be administered following an overnight fast of at least 10 hours and fed study treatments will be administered 30 minutes after the start of a high-fat a meal.
- On the morning of Day of Treatment Period all participants will receive the milvexian mg oral solution, in the fasted state followed 1 hour later by the IV [14C]milvexian μg microdose, containing NMT kBq, infused over 15 minutes.
- On the morning of Day for Treatment Periods participants will receive milvexian SDD capsules, at doses of mg and mg in the fed and fasted states, in an order according to the randomization schedule, with a minimum 72 hour washout between dose administration in each treatment period.
- Participants will be discharged from the clinical unit 72 hours after the final dose of study treatment (ie following Treatment Period).
- There will be a follow up phone call 5 to 7 days post final dose (ie Treatment Period), Day to ensure the ongoing wellbeing of the participants.

[figure not shown]
Table 5.1-1: Treatment Sequences

Sequence number					
1	A	В	С	E	D

Table 5.1-1: Treatment Sequences

Sequence number					
2	A	С	D	В	Е

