3	A	D	Е	С	В
4	A	Е	В	D	С

A: mg milvexian oral solution with mg µg IV microdose; B: mg milvexian SDD fasted; C: mg mg milvexian SDD fed; D: mg milvexian SDD fasted; E: mg milvexian SDD fed. TP: treatment period.

Physical examinations, vital sign measurements, 12-lead electrocardiograms (ECGs), and clinical laboratory evaluations will be performed at selected times throughout the dosing interval. Participants will be closely monitored for AEs throughout the study. Blood and urine samples will be collected for up to 72 hours after study intervention administration for pharmacokinetic (PK) analysis. Less than 550 mL of blood will be drawn from each participant during the study.

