5.4 Scientific Rationale for Study Design

[figure not shown]
The purpose of this study is to assess the absolute oral bioavailability of an SDD formulation of milvexian at a clinically relevant dose range, in the fed and fasted states, and to bridge the exposures seen using the oral solution.

[figure not shown]
Randomization will be used for 4 of the 5 regimens to minimize bias in the assignment of participants to treatment groups, to increase the likelihood that known and unknown participant attributes (eg demographic and baseline characteristics) are evenly balanced across treatment groups, and to enhance the validity of comparisons across dose groups. The regimen containing the radiolabeled intravenous (IV) microdose will not be randomized owing to logistical considerations.

The IV microtracer technique is an established methodology for measuring the IV and oral kinetics of a drug in the same individuals in a single dosing period. The technique involves concurrent administration of a microdose of the drug containing microtracer amounts of ¹⁴C with a single oral therapeutic dose, which avoids the concerns of dose-dependent kinetics when extrapolating IV PK from a microdose, as the systemic exposure is at therapeutic concentrations. Moreover, for this reason the IV administration is timed to coincide with the expected Tmax of the oral dose. This design enables measurement of ¹⁴C-labelled drug in plasma following IV dosing via sensitive accelerator mass spectrometry (AMS) techniques, and measurement of the unlabeled parent in the plasma by standard high performance liquid chromatography mass spectrometry/mass spectrometry (HPLC MS/MS) techniques. Thus, it is possible to obtain the IV PK parameters with

the associated variability and calculate the absolute bioavailability. In addition, because the IV dose administration involves giving a low volume of a low concentration of parent drug, an advantage of this approach is that it is much easier to develop an IV formulation for micro dosing, than it would be for a higher clinical dose.

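### The Frel model cannot estimate any capsule-versus-solution ratio, because the oral solution is given only in the first period and period is a fixed effect; dose normalization for Frel is also not stated

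*Combined protocol and SAP*

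**What the plan says.** The Frel row of Table 10.4.2-1 (Section 10.4.2) promises point estimates and 90% CIs for ratios of geometric means of Cmax, AUC(0-T) and AUC(INF), comparing "each milvexian capsule treatment separately versus mg oral solution". The model is a linear mixed model on log-transformed data "with treatment and period as fixed effects, and measurements within each participant as repeated measures". The food-effect row uses the same model for the fed-versus-fasted comparisons.

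On design, Section 5.4 says: "The regimen containing the radiolabeled intravenous (IV) microdose will not be randomized owing to logistical considerations". Table 5.1-1 lists the sequences as ABCED, ACDBE, ADECB and AEBDC, where A is the oral solution with the IV microdose and B to E are the capsule treatments.

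On dose, Section 5.1 describes "crossover doses of SDD capsules at two dose levels in the fed and fasted state", with one solution dose. Neither the Frel row nor the definition of Frel in Section 9.5 mentions division by dose. Section 3.3.1 groups one oral dose "as SDD capsules in the fed and fasted state, and as the oral solution", which suggests that the solution matches one capsule level.

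**The concern.** A treatment given only in one period, which is also the only treatment given in that period, cannot be separated from that period's effect. The Frel row asks for exactly that separation. Frel is a named secondary endpoint, and Section 5.4 gives bridging to the oral solution as part of the study's purpose, so the printed model fails on a quantity the study sets out to deliver. It fails at every capsule dose, matched or not.

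Dose is a separate matter. One solution dose cannot equal two capsule doses, so at least two of the four contrasts (fed and fasted at one level) are between different doses. If those ratios were left undivided, they would mix relative bioavailability with the dose ratio.

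**Working it through.** **Inputs.** Sequences: Table 5.1-1. Model terms: Table 10.4.2-1. n = 13 evaluable of 16 randomized, intra-subject CV 28.3%, 90% CI, limits 80% to 125%, probability 80%: Section 10.2. Fold increases of 139 (Cmax), 168 (AUC(0-T)) and 102 (AUC(INF)) over a 125-fold dose range, fasted single doses: Section 3.2.1.

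**1. The plan's own precision figure.** The log-scale SD is √ln(1 + 0.283²) = 0.2776. With 12 df, the 90% CI half-width at that SD is t(0.95, 12) × 0.2776 × √(2/13) = 0.194, a factor of 1.214. The probability that the half-width stays within ln 1.25 is P(χ²₁₂ ≤ 12 × [0.2231/0.194]²) = 0.803. This agrees with the stated 80%; n = 12 gives 0.721. The sample-size statement reproduces.

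**2. Estimability.** The fixed effects are an intercept, 4 treatment columns and 4 period columns, 9 in all. A appears in the first period and nowhere else, and nothing else appears there. One can therefore add any constant to all four capsule effects, subtract it from the effects of periods 2 to 5, and leave every fitted value unchanged.
- Rank is 8 of 9, both for 16 participants (4 per sequence) and for 13 (4/3/3/3). With participant effects added at n = 16, it is 23 of 24.
- B−A, C−A, D−A and E−A are not estimable.
- C−B and E−D (fed versus fasted at each dose level) are estimable.

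**3. What the printed model could return.** Assume a true Frel of 1 and log period effects of 0, 0.05, 0.10, 0.05 and 0.15 for periods 1 to 5. These values are illustrative, not from the documents. Dropping the column for period 2, 3, 4 or 5 gives a B/A ratio of 1.05, 1.11, 1.05 or 1.16. With no period term it is exp[(0.05 + 0.10 + 0.05 + 0.15)/4] = exp(0.0875) = 1.09. C/B is 1.00 whichever column is dropped.

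**4. Precision without the period term.** At n = 13 with complete data the residual df are 4 × 12 = 48. The half-width is t(0.95, 48) × 0.2776 × √(2/13) = 0.183, a factor of 1.20.

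**5. Dose.** An undivided ratio equals (capsule dose / solution dose) × Frel. This is an identity and needs no proportionality assumption. Doses are redacted, so for illustration only: with an assumed Frel of 0.80, dose ratios of 0.5, 2 and 4 would print 0.40, 1.60 and 3.20.

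**6. What remains after dividing.** The implied exponents are ln 139/ln 125 = 1.022, ln 168/ln 125 = 1.061 and ln 102/ln 125 = 0.958. If they held for these formulations, the departure r^(b−1) − 1 at an assumed capsule/solution dose ratio r would be:

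| | 2-fold | 4-fold | 8-fold |
|---|---|---|---|
| Cmax | +1.5% | +3.1% | +4.7% |
| AUC(0-T) | +4.3% | +8.9% | +13.6% |
| AUC(INF) | −2.9% | −5.7% | −8.4% |

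**The case against.** On dose, the opposing case is strong. The endpoint is called relative bioavailability, which ordinarily implies dose correction. Section 9.5 defines its parameters in words without formulas, so silence about a divisor there proves little. Section 10.4 calls itself a summary ahead of a SAP that is not in the file. Divided and undivided estimates differ on the log scale by a known constant, so either converts exactly to the other. A reader might infer that the plan intends raw ratios and that Frel at one dose will be wrong by the dose ratio. The documents do not support that. What stands is that the divisor and its proportionality assumption are not written down. Nor should weight rest on the dose grouping in Section 3.3.1: it gives the second capsule dose in the fed state only, while Table 5.1-1 has "D: mg milvexian SDD fasted; E: mg milvexian SDD fed". Those places need reconciling. The count of at least two unmatched contrasts does not depend on that grouping.

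On period, it can be said that a programmer would notice a rank-deficient fit and that the SAP may change the model. Both may happen, but software can also drop a column without comment. Section 10.4 assigns the SAP the selection of participants and the handling of missing, unused and spurious data, not a revision of the model. A dose divisor would not cure the aliasing.

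It is also fair that removing the period term does not remove the confounding. The design causes it, and no choice of model can test it.

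**Conclusion.** The Frel row is wrong as written: 0 of 4 capsule-versus-solution contrasts are estimable from the printed model. This follows from Table 5.1-1 and the model terms alone and depends on no redacted value. The missing statement on dose is a secondary gap of unknown size; the figures in steps 5 and 6 of the working rest on assumed dose ratios, and step 6 also on exponents from end-to-end fasted single-dose data carried over to other formulations and the fed state.

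A reader might go further and infer that the food-effect results, the sample size or the design itself fail. They do not. Both food-effect contrasts are estimable under the printed model, the precision figure reproduces, and Frel can be estimated once the first-period limitation is accepted and stated.

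Severity is minor. Section 10.1 says no hypothesis is formally evaluated, and no decision rule rests on Frel. F by treatment, the primary endpoint, gives AUC-based comparisons of capsule with solution, although these also set later periods against the first. Cmax-based Frel cannot be recovered that way.

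**What to change.** In the Frel row of Table 10.4.2-1:
- Fit the capsule-versus-solution contrasts with treatment as the only fixed effect and participant as the repeated-measures unit. In complete data the point estimates equal those from within-participant log ratios.
- State that the solution is always given in the first period, so Frel is confounded with any difference between the first and later periods, and that this design cannot test for one.
- State that Cmax, AUC(0-T) and AUC(INF) are divided by the administered oral dose before log transformation, and that Frel at the unmatched dose assumes dose proportionality. Put the same divisor in the Frel definition in Section 9.5.

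Keep treatment plus period for the food-effect row.

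The cost is one changed model line, a few sentences and three derived variables, with no new data. The downside is that Frel then relies on there being no first-period effect, a limit the design already imposes. Differences among the four later periods are also left unadjusted; they average out across capsule treatments when the sequences are balanced, and only approximately after uneven dropout.
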